3.3 Randomization

Provider-side treatments will be cluster randomized at the practice level. Randomization will stratify across practices by number of diabetic patients (cluster size), and will be conducted using a random number generator at the outset of the study. Reminder messaging treatments will be assigned alphabetically by first two letters of patient last name, as it is logistically infeasible to do individual level patient messaging without sorting on an existing field in the patient's EHR. There are some concerns that ethnicity could correlate with assignment based on last name spelling, so this form of assignment is "pseudo-random". However, the patient's race/ethnicity recorded in the medical record will be controlled for in the analysis. Causal interpretation of the results of the reminder messaging portion of the experiment will thus require the assumption that grouped last name spelling is not independently related to likelihood of flowsheet adoption.

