4.1 Sample Size

Non-pregnant adult patients of Inova primary care physicians with a current diabetes mellitus diagnosis and active MyChart account at time of treatment administration will be included in the study. The estimated number of patients is around 7200, from 71 primary care physicians across 24 selected Inova primary care practices.

Power Calculations

Power calculations were performed using the “clustersampsi” command in Stata. Knowledge of available sample and estimates/assumptions of control outcome mean, variance, and intraclass correlation were used to calculate a minimum detectable effect size for the key outcomes of flowsheet adoption (extensive margin, dichotomous rate of adoption) and changes in mean A1c.

Flowsheet Adoption: Practice Level Treatment-Control Comparison

Sample Size: 7200

Number of Treatment Arms: 2

Number of Clusters: 24

Assumed Control Adoption Rate: 2%

Assumed Intra-Cluster Correlation (within practices): 0.1

Minimum Detectable Effect: **9.5 percentage point increase in flowsheet orders**

Mean HbA1c: Practice Level Treatment Control Comparison

Sample Size: 7200

Number of Treatment Arms: 2

Number of Clusters: 24

Assumed Control HbA1c Mean: 6.74

Assumed Control HbA1c Standard Deviation: 1.39

Assumed Intra-Cluster Correlation (within practices): 0.07

Assumed Baseline Correlation: 0.80

ITT Minimum Detectable Effect: **0.27 change in A1c**

Flowsheet Adoption: Individual Level Comparison between Messaging Assignment Groups in Treatment Practices

Sample Size: 3600

Number of Arms (including no reminder): 4

Assumed No Reminder Adoption Rate: 20%

Minimum Detectable Effect: **5.5 percentage point increase in use of flowsheets when compared to no reminder**

Justification

The sample size represents the entire population of Inova primary care patients with diabetes who have active MyChart accounts and are therefore able to access the blood glucose tracking feature. The minimum detectable effects resulting from power calculations above are in-line with similar studies cited in the protocol background. Metastudy reviews of the effect of self monitoring of blood glucose found a 0.33 point change in A1c.

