4.2 Method of Data Analysis

All data analyzed in this study will be administrative health and use data that is collected as part of routine medical care and record keeping. EPIC has offered to build the SQL queries required to produce the outcome datasets described in this protocol. Outcomes listed in Section 3.4. will be analyzed using regression analysis, including (a) a version with no covariates, (b) a version controlling for patient age/gender, race/ethnicity, A1c at baseline, days since most recent office visit at baseline, and doctor fixed effects. A flag identifying patients who are eventual participants of "Impact of Innovative Interventions on Diabetic Adherence with Digital Sensors" (a study recently submitted to the IRB that may have limited overlap with this population) will also be included in the controls. For outcomes indicating analysis of practice level treatment and control groups, standard errors will be clustered at the practice level.

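### If doctors are nested in practices, doctor fixed effects leave the adjusted treatment-versus-control effect unidentified; limit them to the reminder comparisons

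*Combined protocol and SAP*

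**What the plan says.** Section 4.2 sets one analysis rule for every outcome: "Outcomes listed in Section 3.4. will be analyzed using regression analysis, including (a) a version with no covariates", followed by a version (b) with patient age/gender, race/ethnicity, "A1c at baseline, days since most recent office visit at baseline, and doctor fixed effects". A flag for patients in an overlapping study "will also be included in the controls". Practice-level comparisons are singled out only for their standard errors: "For outcomes indicating analysis of practice level treatment and control groups, standard errors will be clustered at the practice level". Nothing exempts them from the doctor fixed effects.

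Most Section 3.4 outcomes compare treatment with control practices: adoption, flowsheet orders, A1c, doctor-patient contacts and medication changes. The others compare reminder groups within treatment practices.

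On assignment, Section 3.3 states: "Provider-side treatments will be cluster randomized at the practice level", stratified by practice size. Section 3.1.2 assigns reminders to individual patients. Section 4.1 describes about 7,200 patients "from 71 primary care physicians across 24 selected Inova primary care practices". The A1c power calculation there lists "Assumed Baseline Correlation: 0.80" and gives a minimum detectable effect (MDE) of 0.27.

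**The concern.** A fixed effect for each doctor absorbs everything that is constant within a doctor. Practice-level treatment is constant within a doctor whenever that doctor works in a single practice. Version (b) would then remove the contrast it is meant to estimate. This applies to the dichotomous, count and quantile outcomes as well as to mean A1c, and neither more patients nor clustered standard errors would restore the contrast.

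Software may drop the treatment term. It may instead drop an extra doctor indicator and print a coefficient labelled as treatment that has no such meaning. Either way the plan lacks a usable adjusted estimate for the practice comparisons, and the choice of a replacement is left open.

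**Working it through.** **1. Identification.** Let D_ij = 1 if patient i belongs to doctor j, and T_i = 1 if the patient's practice is treated. Under nesting, T_i is the sum of D_ij over the treated doctors. For any constant c, adding c to the treatment coefficient and subtracting c from each treated doctor's effect leaves every fitted value unchanged. The data therefore cannot determine the coefficient.

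Numerical check on a constructed layout (7,200 patients, 71 doctors nested in 24 practices, 12 treated):

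| Model | Columns | Rank |
|---|---|---|
| Doctor indicators + treatment | 72 | 71 |
| Full version (b): 71 doctors, treatment, age, sex, 4 race indicators (assumed coding), baseline A1c, days since visit, flag | 81 | 80 |
| Replacement: 6 size strata of 4 practices (assumed), treatment, same 9 covariates, no doctor effects | 16 | 16 |
| Reminder comparison: 36 treated-arm doctors in this draw, 3 reminder indicators, same 9 covariates | 48 | 48 |

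The first two models are one short of full rank. The largest residual of treatment on the doctor indicators is 1.6e-15, which is zero to machine precision.

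**2. What a printed coefficient would mean.** With an intercept, software must omit one treated and one control doctor as references. In this layout that gives 36 × 35 = 1,260 possible pairs. In 500 simulated A1c datasets (the plan's SD 1.39, ICC 0.07 and baseline correlation 0.80; true effect -0.27; models with baseline A1c and the flag), the coefficient within one dataset ran on average from -1.15 to +0.62 over these pairs, and 21% of choices had the wrong sign. Two pairs in one dataset gave +0.026 and -0.143 with identical fitted values. The replacement model on the same data gave a mean of -0.265 (SD 0.091). The range depends on the constructed layout; the arbitrariness does not.

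**3. If nesting fails.** With equal panels (7,200/71, about 101 patients), 1 to 5 doctors working in both arms would make 1/71 = 1.4% to 5/71 = 7.0% of patients the only source of the estimate.

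**4. Link to the stated A1c MDE.** Two-sided 0.05 and 80% power are assumed, because the plan states neither. There are 12 practices of 300 patients per arm (7,200/24 = 300).

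MDE = (t22,0.975 + t22,0.80) × 1.39 × f × sqrt{[1 + 299 × 0.07]/300 × [1/12 + 1/12]}

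The design effect is 1 + 299 × 0.07 = 21.93, and the square root is sqrt(0.0731 × 0.1667) = 0.1104.

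| Analysis | f | t, 22 df | z |
|---|---|---|---|
| Baseline-adjusted | sqrt(1 - 0.80²) = 0.600 | 0.270 | 0.258 |
| Change from baseline, ICC still 0.07 | sqrt(2 × 0.20) = 0.632 | 0.285 | 0.272 |
| End-of-period mean, version (a) | 1 | 0.450 | 0.430 |

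The plan's 0.27 is reproduced by the baseline-adjusted analysis with t critical values. The same t convention fits the plan's adoption MDE. With ICC 0.1 the design effect is 30.9, and 3,600/30.9 = 116.5 effective patients per arm. Unpooled variances then give 9.45 points with t and 8.85 with z, against the stated 9.5.

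**The case against.** - **Version (a) survives, and adoption comes first.** Section 1.1 makes the health analyses conditional on a significant rise in adoption, and the 9.5-point adoption MDE uses no baseline correlation. This stands: the unadjusted, clustered intention-to-treat comparison is valid for every practice-level outcome, and for adoption version (b) is a supporting analysis.
- **The fault can be found without outcome data.** This also stands. Doctor and practice identifiers reveal the collinearity, so nothing forces a change after results are seen. It is a reason to correct the text now. The list of models is not plainly exhaustive, but no other adjusted model is specified.
- **Nesting is inferred.** True: Section 4.1 gives counts only. The non-nested case does not rescue version (b), because the estimate would then come from the few doctors who work in both arms.
- **The 0.27 might describe an unadjusted change score.** With z values, change from baseline gives 0.272, and Section 4.1 speaks of change in A1c. However, z gives 8.85 points for adoption, further from the stated 9.5 than the 9.45 from t, and under t the change score gives 0.285. Section 3.4 also lists mean A1c at the end of each period. The baseline-adjusted reading fits better, although alpha and power are not stated.
- **A before-after model may have been meant.** A treatment-by-period term would be identified alongside doctor effects. The plan specifies none, and Section 3.4 describes comparisons at or during post-baseline periods.
- **Stratum indicators are not needed for identification.** Correct: removing the doctor effects is enough. The strata are included because randomisation used them.

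**Conclusion.** The concern holds and should be fixed before analysis. If each doctor works in one practice, version (b) cannot estimate the treatment effect for any treatment-versus-control practice outcome: it is one rank short, by algebra and not by sampling chance. If a few doctors work in both arms, it estimates something other than the randomised comparison. Version (a) and the reminder comparisons are sound.

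The practical loss is greatest for A1c. Under the assumptions above, the design detects 0.27 with baseline adjustment and about 0.45 without it on the end-of-period mean. The 0.33-point effect that Section 4.1 cites as its justification lies between the two. The simulated range of coefficients is illustrative and is not a forecast for this trial.

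**What to change.** Amend Section 4.2 as follows.

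1. Use doctor fixed effects only in the reminder comparisons within treatment practices.
2. For treatment-versus-control practice comparisons, define version (b) as age/gender, race/ethnicity, baseline A1c, days since most recent office visit, the overlap-study flag already planned, and indicators for the practice-size randomisation strata. Include no doctor fixed effects, and cluster standard errors by practice.
3. State in Section 4.1 that the 0.27 A1c MDE refers to this baseline-adjusted model.

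The cost is SAP wording only. Every variable is already planned or was used in the randomisation, so no new data are needed.

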2.3 Duration of Study

Primary care practices identified in the treatment group will be encouraged to place bulk orders for electronic glucose flowsheets over a period of two weeks. Patients will be actively encouraged to use flowsheets for 12 weeks following the administration period. Outcome data will be collected for a total of 38 weeks:

- (a) 12 weeks retrospective at baseline
- (b) 2 week administration period
- (c) 12 week implementation period
- (d) 12 week follow up period

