3.4 Endpoints/Outcomes Measurements

Hypothesis: Interfacing with primary care practices to encourage physicians to implement default online orders of blood glucose flowsheets and informational messaging for all patients with diabetes will increase patient adoption.

Outcome Measures: Comparison of individuals between treatment and control practices-- (a) fraction of patients entering blood glucose measurements into MyChart flowsheets during implementation period & follow-up period (dichotomous), (b) mean number of flowsheet entries during implementation period and follow-up period (c) fraction of patients for whom order is placed by doctor

Hypothesis: Additional reminder messaging to patients that (1) emphasizes the value of tracking blood glucose data to the patient OR (2) emphasize the value of tracking blood glucose data to the doctor OR (3) informs patient of their selection for a chance to receive an award conditional on tracking will increase adoption relative to no reminder messaging.

Outcome Measure: Comparison of individuals across reminder messaging assignment groups (within treatment practices)-- (a) fraction of patients entering blood glucose measurements into MyChart flowsheets during implementation period & follow-up period (dichotomous), (b) mean number of flowsheet entries during implementation period and follow-up period

Hypothesis: Promotion of adoption of electronic blood glucose tracking through the means described above will result in the following intent-to-treat effects:

(a) reduction in patient A1c

Outcome Measures: Intent to treat comparison of individuals between treatment and control practices of the following measures at the end of the intervention period and follow-up period: (1) Mean A1c (2) Quartiles of A1c using quantile regression analysis (3) fraction of patients experiencing improvement [reduction] in A1c from baseline (dichotomous) (4) fraction of patients below benchmark 7.0% A1c (dichotomous)

(b) increase in frequency of doctor-patient interaction

Outcome Measures: Intent to treat comparison of individuals between treatment and control practices of the following measures during the intervention period and follow-up period: (1) number of securing messaging (2) number of phone interactions, and (3) number of in-office appointments

(c) changes to treatment plan path

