Outcome Measure: Intent to treat comparison of individuals between treatment and control practices of number of alterations to patient prescriptions/medication list during the intervention period and follow-up period

Hypothesis: Reminder messaging treatments that induce more intensive use of flowsheets will lead patients to experience larger effects as described above.

Outcome Measure: Intent to treat and treatment on the treated comparison of individuals across reminder messaging assignment groups (within treatment practices)-- reduction in A1c, increase in frequency of doctor-patient interactions, changes to treatment plan path (outcomes as described above in a-c)

Hypothesis: Entries of blood glucose data will be predictive of A1c and will lower over the study period.

Outcome Measure: Descriptive analysis of flowsheet entry values in the treatment group during the implementation and follow-up period.

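### The practice-level tests of contact and medication changes (H1.2.3(b), (c)) use post-launch counts without the patient's pre-launch count, which gives up precision that the 12-week baseline window could supply

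*Combined protocol and SAP*

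**What the plan says.** Section 2.3 states that "Outcome data will be collected for a total of 38 weeks", the first part being "12 weeks retrospective at baseline". It does not list the variables.

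Section 3.4 gives hypothesis (b) as an "increase in frequency of doctor-patient interaction" and compares practices on an intent-to-treat basis "of the following measures during the intervention period and follow-up period: (1) number of securing messaging (2) number of phone interactions", with in-office appointments as the third measure. For hypothesis (c) the measure is the "number of alterations to patient prescriptions/medication list during the intervention period and follow-up period". No change from baseline is defined for any of the four. For A1c, by contrast, section 3.4 includes the fraction of patients who improve from baseline.

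Section 4.2 plans regressions without covariates (version a) and with covariates (version b). Version (b) has age and gender, race/ethnicity, "A1c at baseline, days since most recent office visit at baseline, and doctor fixed effects", and a flag for participation in another study. Standard errors for practice-level comparisons are clustered by practice. Section 3.3 stratifies the practice randomisation on number of diabetic patients only.

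**The concern.** Practices may differ lastingly in how much they use portal messages and the telephone, how often they see patients and how often they alter prescriptions. With roughly 12 practices per arm and stratification on size alone, one arm can by chance receive more of the practices that are already high in contact. Clustered standard errors allow for that variation but do not reduce it. A prior count of the same outcome is the direct measure of it.

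Days since the last office visit is a partial stand-in for appointment frequency. It does not measure messages, calls or medication changes.

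At stake is the sharpness of the mechanism results: if A1c moves, or does not, these four outcomes are meant to help explain why. They have no power calculation, so any avoidable widening of their intervals goes unnoticed at the planning stage.

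**Working it through.** **Inputs.** Section 4.1: 7,200 patients, 24 practices, 71 physicians; for A1c, SD 1.39, intra-cluster correlation (ICC) 0.07, baseline correlation 0.80, stated minimum detectable effect (MDE) 0.27. Assumed here: equal sizes, so k = 12 practices per arm and m = 300 patients per practice; two-sided 5% level and 80% power, neither of which is stated; t quantiles on 24 − 2 = 22 degrees of freedom. Sections 2.2 and 3.2 speak of 27 practices; the power section's 24 is used.

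**1. Reproduce the plan's A1c figure.**

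MDE = (t₀.₉₇₅ + t₀.₈₀) × SD × √(2[1 + (m − 1)ICC]/(km)) × √(1 − r²)

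- Design effect: 1 + 299 × 0.07 = 21.93
- Standard error without baseline: 1.39 × √(2 × 21.93/3600) = 0.1534
- Quantiles: 2.074 + 0.858 = 2.932
- r = 0: 2.932 × 0.1534 = 0.450
- r = 0.80: 0.450 × 0.60 = 0.270, which matches the stated 0.27

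So the plan's A1c figure already credits a baseline value of the outcome. Without it, power at 0.27 would be about 38%.

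**2. Where the error variance sits.** The between-practice share of the variance of a practice mean is m × ICC/[1 + (m − 1)ICC].

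| ICC | Share |
|---|---|
| 0.01 | 3/3.99 = 75% |
| 0.07 | 21/21.93 = 96% |
| 0.10 | 30/30.9 = 97% |

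In the practice comparison, standing practice differences dominate the error even at a small ICC.

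**3. Gain for the count outcomes.** The documents give no SD, ICC or r for these counts, so both are varied over assumed ranges and the MDE is in SD units.

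| r | √(1 − r²) | Fall in standard error | MDE at ICC 0.01 | MDE at ICC 0.07 | MDE at ICC 0.10 |
|---|---|---|---|---|---|
| none | 1 | – | 0.138 | 0.324 | 0.384 |
| 0.3 | 0.954 | 5% | 0.132 | 0.309 | 0.366 |
| 0.5 | 0.866 | 13% | 0.120 | 0.280 | 0.333 |
| 0.7 | 0.714 | 29% | 0.099 | 0.231 | 0.274 |
| 0.8 | 0.600 | 40% | 0.083 | 0.194 | 0.231 |

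Here r is the correlation between a practice's mean count before and after launch. It is a weighted average of the practice-level and patient-level correlations, with the shares in step 2 as weights. At ICC 0.07, a practice-level correlation of 0.8 and a patient-level one of 0.5 give 0.958 × 0.8 + 0.042 × 0.5 = 0.787. The practice level therefore decides the gain.

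**4. Can the covariate go into version (b)?** Take the 71 doctors as nested in 24 practices. The matrix of doctor effects has rank 71, and still has rank 71 when the practice treatment indicator is added. The treatment effect cannot be estimated in that model from post-launch data. A practice mean is likewise constant within doctor and is absorbed. The covariates need a model without doctor effects, or one that uses both periods.

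**5. The two-period alternative.** A treatment-by-post contrast behaves like a change score. With equal windows its factor is √(2(1 − r)): 1.18 at r = 0.3, 1.00 at 0.5, 0.77 at 0.7 and 0.63 at 0.8. It beats the post-launch comparison only if r exceeds 0.5.

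**The case against.** The strongest case against is that nothing here is invalid, and that stands. Section 3.4 defines the test as a comparison between randomised groups, so an increase means more contact than in control practices, not a rise within a patient. The test is unbiased in expectation, and the clustered errors carry the chance variation between practices. A reader might infer that the post-launch comparison is biased, or that it fails to address the hypothesis; the documents support neither.

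It can also be said that doctor fixed effects in version (b) already remove practice habits. They do, but in the practice comparison they remove the treatment effect with them. Any version that can be estimated leaves those differences in the error.

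Three further limits stand:

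- The size of the gain is unknown. The 0.80 in section 4.1 is for A1c, a laboratory measure, and cannot be carried over to counts.
- That the baseline window holds these counts is a reasonable inference from the words on outcome data, not a statement. Section 4.2 says only that the EHR vendor has offered to build the queries.
- These are mechanism outcomes, which section 1.1 takes up after an adoption effect, and the power calculation does not cover them.

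**Conclusion.** The point holds for the practice-level comparisons in H1.2.3(b) and (c), as avoidable loss of precision and unadjusted chance imbalance. Over an assumed r of 0.3 to 0.8, mainly at practice level, the standard error would fall by 5% to 40%. This rests on equal practice sizes, doctors nested in practices, and the prior counts being retrievable.

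A reader might extend the argument to H1.2.4. The documents do not support that: section 3.4 compares reminder groups within treatment practices, where doctor effects can be estimated and already remove practice habits. The patient's own prior count could still add precision there, but practice imbalance is not a reason for it.

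The change is worth making because it is cheap and must be fixed before results are seen.

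**What to change.** 1. Confirm that the query returns secure messages, phone contacts, appointments and medication-list alterations for the 12 weeks before the administration period, and add them if it does not.
2. For each H1.2.3(b) and (c) outcome, pre-specify an adjusted practice-level model with the patient's own count of that outcome in those 12 weeks and the practice mean of that count. Keep the two administration weeks out of the baseline count. Omit doctor fixed effects from this model, and keep errors clustered by practice.
3. As an alternative, use a patient-by-period model with a treatment-by-post term, in which doctor effects can stay, again with practice-clustered errors. Choose it knowing that it loses precision if r is below 0.5.
4. Put counts on a common time base. Section 3.4 refers to an intervention period that section 2.3 does not define: it is 12 weeks if it means implementation only, and 2 + 12 = 14 if it includes administration.
5. For H1.2.4, the patient's own prior count may be added for precision only.

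Cost: two covariates per outcome and possibly a longer query window. The practice mean uses about one of 22 between-practice degrees of freedom, which moves the quantile sum from 2.932 to 2.939 (22 to 21 degrees of freedom), or about 0.2%. No new patients or procedures are needed.

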1.2 Hypotheses

1.2.1 Interfacing with primary care practices to encourage physicians to implement default online orders of blood glucose flowsheets and informational messaging for all patients with diabetes will increase patient adoption (as defined above).

1.2.2. Additional reminder messaging to patients that (1) emphasizes the value of tracking blood glucose data to the patient OR (2) emphasize the value of tracking blood glucose data to the doctor OR (3) informs patient of their selection for a chance to receive an award conditional on tracking will increase adoption relative to no reminder messaging.

1.2.3 Promotion of adoption of electronic blood glucose tracking through the means described above will result in the following intent-to-treat effects:

- (a) reduction in patient A1c
- (b) increases in frequency of doctor-patient interaction
- (c) changes to treatment plan path

1.2.4 Reminder messaging treatments that induce more intensive use of flowsheets will lead patients to experience larger effects as described in 1.2.3.

1.2.5 Entries of blood glucose data will be predictive of A1c on average and will lower over the study period.

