5.1 Risks

The risks to participation in this study are minimal. The randomized encouragement design means that doctors will make the final determination of whether use of electronic blood glucose flow sheets is suitable for the patient. The study does not advise against or preclude the provider or patient from switching to alternative methods for self monitoring of blood glucose, or using other forms of treatment concurrently. Previous research has shown positive health effects of self monitoring of blood glucose, and it is a recommended treatment for diabetes. However, one low risk area is potential loss of privacy. The risk will be minimized by implementing an adequate plan to protect the identifiers from improper use and disclosure: a limited dataset will be created and made available to authorized researchers via remote access on Citrix. Data will be fully anonymized and linkages to identifying information will be permanently destroyed three (3) years after the conclusion of the study. Protected health information will not be reused or disclosed to any other person or entity, except as required by law, or for authorized oversight of the research project.

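### The adjusted model controls for eventual participation in another study, with no requirement that joining precede randomisation, so adjusted estimates can be biased if assignment affects who joins

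*Combined protocol and SAP*

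**What the plan says.** Section 4.2 plans two regressions for each outcome in section 3.4. The first is "a) a version with no covariates". Version (b) adjusts for age/gender, race/ethnicity and "A1c at baseline, days since most recent office visit at baseline, and doctor fixed effects". The section then adds "A flag identifying patients who are eventual participants of" a further study of diabetic adherence, described as "a study recently submitted to the IRB that may have limited overlap with this population) will also be included in the controls".

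Two of the covariates are tied to baseline in so many words. The flag is not, and no date limits it. Section 3.3 says that practice randomisation "will be conducted using a random number generator at the outset of the study". Section 4.2 does not say whether (a) or (b) is the primary analysis. The documents give no recruitment route, eligibility, sites or dates for the other study.

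**The concern.** Covariates fixed before assignment are safe to adjust for. A covariate determined after assignment is safe only if assignment does not affect it. As worded, the flag marks anyone who joins the other study at any time, including during implementation or follow-up.

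The intervention could plausibly change joining. Treatment practices are contacted, their physicians receive reports and alerts, patients are messaged, and section 1.2 itself hypothesises "increases in frequency of doctor-patient interaction". More contact and more engagement could alter who is approached for, or agrees to enter, a sensor-based adherence study. If so, holding the flag constant removes any part of the intention-to-treat effect that runs through joining. It also compares joiners and non-joiners who differ between arms in unmeasured engagement.

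If joining is unrelated to assignment, omitting the flag causes no bias, so the flag is not needed for validity.

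**Working it through.** **1. Which analyses are exposed.**
- Version (a) has no covariates, so the flag cannot affect it.
- In version (b), practice-level treatment is constant within a practice. If each of the 71 physicians in section 4.1 works in only one of the 24 practices (an assumption; the documents do not say), the doctor fixed effects absorb the treatment indicator. A rank check gives 71 with the indicator and 71 without it, so the practice-level effect is not estimable in (b) as written.
- The reminder comparisons are made within treatment practices and survive doctor fixed effects. Section 3.3 assigns reminders by surname and promises to control for race/ethnicity. In section 4.2 that control appears only in (b), where the flag also sits.

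**2. Yardstick: the plan's own A1c figure.** Inputs from section 4.1: 7200 patients, 24 clusters (300 per cluster), SD 1.39, intra-cluster correlation 0.07, baseline correlation 0.80. Two-sided 5% and 80% power are assumed, because the plan states neither.
- Design effect = 1 + 299 × 0.07 = 21.93
- Residual SD = 1.39 × √(1 − 0.80²) = 0.834
- MDE = (2.074 + 0.858) × 0.834 × √(2 × 21.93 / 3600) = 0.270, using t quantiles on 22 df. The stated figure is 0.27, so it reproduces.

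**3. Formula for the shift.** In least squares with treatment and the flag only:

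adjusted effect − unadjusted effect = −(joining rate, treated − joining rate, control) × (within-arm outcome difference, joiners − non-joiners)

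If the arms join at the same rate, the shift is zero.

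**4. Size for A1c.** Simulation of 4 million patients with residual SD 0.834 and no direct treatment effect. Assumptions that are not in the documents: an unmeasured engagement factor raises joining with an odds ratio of 3 per SD and correlates −0.3 with residual A1c; the other study's own effect on A1c is 0 or −0.5. Overlap means the joining rate in the control arm. A positive shift is towards higher A1c under treatment.

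At 2% overlap:

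| Odds ratio, treatment on joining | Joining, control v treated | Shift, other study's effect 0 | Shift, other study's effect −0.5 |
|---|---|---|---|
| 1 | 2.0% v 2.0% | 0.000 | 0.000 |
| 1.5 | 2.0% v 2.9% | 0.0024 | 0.0070 |
| 2 | 2.0% v 3.8% | 0.0047 | 0.0137 |
| 3 | 2.0% v 5.45% | 0.0089 | 0.0259 |

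Check against step 3, odds ratio 2, no effect of the other study: 0.0047 / (0.0381 − 0.0201) = 0.26, the implied A1c gap between joiners and non-joiners.

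Over odds ratios of 1.5 to 3, the shift at 2% overlap is 0.0024 to 0.0259, that is 0.0024 / 0.27 = 0.9% to 0.0259 / 0.27 = 9.6% of the MDE. With more overlap the range is 0.005 to 0.056 at 5% and 0.009 to 0.090 at 10%.

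**5. Bound for adoption in the reminder arms.** No simulation was run for this outcome. For a yes/no outcome the gap between joiners and non-joiners cannot exceed 1, so by step 3 the shift cannot exceed the difference in joining between the two arms compared. Borrowing the joining rates above, that is at most 3.81 − 2.02 = 1.8 percentage points at odds ratio 2, against the stated MDE of 5.5 points. The actual shift would be smaller unless joining and adoption coincided completely.

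**The case against.** **The causal link is not documented.** The plan gives little more about the other study than its title, its recent submission for review and its possible limited overlap. If it recruits by a route unrelated to flowsheet promotion, the bias is about zero. This stands. A reader might infer that treatment does change joining, and that the adjusted results are therefore biased. The documents support only that they can be.

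**The timing is not established.** Eventual may be relative to the date of writing, and joining could be complete before this trial's administration period. This also stands. In that case limiting the flag to enrolment before randomisation changes little or nothing. The plan as written does not ensure it.

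**The flag has a sensible purpose.** Section 5.1 says the study does not preclude switching methods of self-monitoring "or using other forms of treatment concurrently", and with only 24 practices another study's intervention could be unevenly spread by chance. That is a fair reason to look at the flag. It is not a reason to put a possibly post-assignment variable in the main model.

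**Version (a) is already planned.** It protects the practice-level comparison, and a gap between (a) and (b) could reveal a material distortion. The protection is partial, because no version is named as primary and version (a) lacks the ethnicity control that section 3.3 relies on for the reminder comparisons.

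**Conclusion.** The concern holds as a conditional one, and it is minor. The flag has no baseline limit. If joining follows assignment and responds to it, the version (b) estimates can be biased, and following the plan gives no safeguard. Version (a) is not affected. The reminder comparisons are the most exposed if doctor fixed effects absorb practice assignment.

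The size is unknown. Under the assumptions shown, it is roughly 0.002 to 0.03 A1c points at 2% overlap, and about zero if joining does not depend on assignment.

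Two larger readings are tempting and are not supported:
- Joining rates of 1% v 4% or 1% v 10%, with a 0.5-point A1c gap, would give shifts of 0.03 × 0.5 = 0.015 or 0.09 × 0.5 = 0.045. These rates imply odds ratios of (0.04/0.96) / (0.01/0.99) ≈ 4 and (0.10/0.90) / (0.01/0.99) = 11. At 10%, some 360 of 3600 treated patients would join, which sits badly with limited overlap.
- The shift could be set against a diluted effect, such as 0.095 × 0.33 ≈ 0.03 or (0.20 − 0.02) × 0.33 ≈ 0.06 from figures in section 4.1, which makes it look large. The plan states no such expected effect. Its own A1c yardstick is 0.27.

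**What to change.** In section 4.2:

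- Leave the flag out of the main adjusted model, or define it only by enrolment in the other study before practice randomisation. If nobody has enrolled by then, the two are the same.
- State whether version (a) or (b) is primary for each comparison.
- Tabulate joining by practice arm and by reminder arm.
- Show the model with the flag as now worded only as a labelled sensitivity analysis.
- Do not rely on excluding later joiners. That conditions on the same post-randomisation event and can carry the same bias.

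The change is about one line of text plus a table. It needs no data beyond the flag already planned and the date of joining, and it alters no stated sample size or minimum detectable effect. The downside is that a chance imbalance across 24 practices in the other study's intervention would go unadjusted in the main model; the sensitivity analysis would show it.
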